## 7.2 Objectives and Analysis Plans

### 7.2.1 Primary Objective and Analysis Plan

The primary objective of the study is to determine the safe reduction of the number of fractions (10, 8, or 5), that may be delivered safely in resected HNSCC patients with intermediate pathologic risk features.

The minimum number of safe fractions will be determined as the radiation dose at which there is no more than a 33% rate of dose-limiting toxicity (DLT) up to 12 months after completion of radiation treatment (to allow for the development of late toxicities from radiation treatment) using the TITE-CRM design.

A DLT will be defined for the purposes of this protocol as an inability to complete radiation treatment within 30 days of the start of radiotherapy not deemed to be related to disease progression or unrelated death, unacceptable toxicity within one year of treatment (Grade 4+ toxicity) probably or definitely related to radiation treatment as deemed by the treating physician, or a death within one year of treatment deemed probably or definitely related to treatment. Expected Grade 3 acute toxicities typical of head and neck radiation that resolve within 90 days of treatment, including acute dermatitis, acute mucositis, feeding tube placement, electrolyte abnormalities, pain requiring narcotic medication and dehydration requiring IV hydration will **NOT** be considered DLTs. Grade 4+ late toxicities that may be considered a DLT of radiation include but are not limited to:

- Chondronecrosis of the laryngeal cartilages
- Laryngeal edema requiring tracheostomy
- Carotid blowout syndrome or other life-threatening vascular bleed
- Aspiration pneumonia requiring ICU admission not related to tumor progression
- Chronic non-healing wound or soft tissue necrosis requiring flap reconstruction
- Brainstem necrosis
- Radiation myelopathy

Death deemed unrelated to radiation (such as death due to malignancy or other comorbidity) will not be considered a DLT.

All patients who initiate radiation therapy will be evaluable for the primary endpoint as long as they initiate radiation therapy.

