## **7 STATISTICAL CONSIDERATIONS**

### **7.1 Study Design**

This is a Phase I dose-hypofractionation trial of radiation dose using a novel radiation treatment regimen called HART-HN. The primary objective of the study is determine the safe reduction of the number of fractions (10, 8, or 5), of the HART-HN regimen, that may be delivered safely in resected HNSCC patients with intermediate pathologic risk features, using the Time-to-Event Continuous Reassessment Methodology design. This will be determined as the radiation dose with the minimum number of fractions at which there is no more than a 33% rate of dose-limiting toxicity (DLT) up to 12 months after completion of radiation treatment (to allow for the development of late toxicities from radiation treatment). There will be three radiation dose levels (all with a BED3 of approximately 100 Gy) evaluated to the operative bed: 42 Gy in 10 fractions (Dose Level 1), 39 Gy in 8 fractions (Dose Level 2) and 32.5 Gy in 5 fractions (Dose Level 3). The total sample size for this study is 18 patients to be recruited over 12 months.

TITE-CRM is an adaptive Phase I trial design methodology which allows for MTD-finding by weighting the follow-up contribution of previously enrolled patients to the selection of the dose level for each newly enrolled patient. If a patient dies of disease progression without evidence of radiation-related toxicity, they will be censored for

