toxicity at the time point of last follow-up. Thus, TITE-CRM allows for dose modification even if patients have not completed the entire follow-up period. At the enrollment of each new patient, beyond the three initial patients who will receive the lowest dose of 42 Gy), all available follow-up for all patients already on study will be used to determine the dose level for the newly enrolled patient based on the TITE-CRM methodology. For example, if three patients are enrolled every two months, by month seven, the first patient (who enrolled in month 1) provides up to 6 months of follow-up whereas the ninth patient (who enrolled in month 6) provides only about 1 month of follow-up. All available follow-up data from the first nine patients will be used by the TITE-CRM model to make a decision on the dose for the tenth patient. Unlike a standard 3+3 design, the TITE-CRM model may maintain the current dose level, increase the dose level or decrease the dose level based on all available follow-up data at the time of enrollment of the tenth patient.

To implement the TITE-CRM model, we will be using the `titecrm` function from the R package `dform`. An unconstrained TITE-CRM model potentially allows for rapid early dose escalation from Dose Level 1 to 3. To prevent this overly aggressive dose escalation we will require at least 3 sequential patients at each dose level, prior to escalating dose. Further, in the case of rapid enrollment of 3 sequential patients at a new dose level, enrollment will be paused until one of these patients experiences a DLT or a minimum of 3 months elapses from the initiation of radiation treatment for these 3 patients.

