### 7.2.2 Secondary Objectives

1. To evaluate the efficacy of the HART-HN regimen at the minimum number of safe fractions at 1-year as measured by locoregional control and overall survival
  - a. To estimate 1-year locoregional recurrence, patients will be followed for locoregional recurrence during the 12-month follow-up period with death as a competing risk using the methodology of Fine and Gray. Cumulative incidence curve will be plotted to describe dynamics of locoregional recurrence over time.
  - b. To estimate 1-year overall survival, the Kaplan-Meier methodology will be used.
2. To assess patient quality of life during and after the HART-HN regimen at the minimum number of safe fractions as measured by a battery of quality of life and functional metrics.
  - a. Quality of life changes will be determined by measuring the following quality of life/toxicity scores at the time points specified in the study calendar: CTCAE version 5.0 scores, composite FACT-HN scores, composite MDADI scores, opioid use, EAT-10 questionnaire scores, Functional Oral Intake (FOIS) scores and Dynamic Imaging Grade of Swallowing Toxicity (DIGEST) grading. QOL measures will be summarized by descriptive statistics; no inferential statistics or hypothesis testing will be performed. The proportion of missing responses will be reported on QOL and functional measures.
  - b. To determine changes in quality of life and toxicity scores, longitudinal plots of these scores will be used to determine whether these return to baseline or improve after treatment.

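### The primary rule sets no minimum number of patients treated at the declared level, so 8 or 5 fractions can be declared safe with 0 to 2 patients treated there

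*Combined protocol and SAP*

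**What the plan says.** Section 7.2.1 defines the primary result by the modelled toxicity rate alone: "The minimum number of safe fractions will be determined as the radiation dose at which there is no more than a 33% rate" of DLT. The window is given as "no more than a 33% rate of dose-limiting toxicity (DLT) up to 12 months after completion of radiation treatment". Section 7.1 has the same rule with the direction made explicit: "This will be determined as the radiation dose with the minimum number of fractions at which there is no more than a 33% rate".

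The design around it, from 7.1:
- Size: "The total sample size for this study is 18 patients to be recruited over 12 months", spread over three levels with no allocation per level.
- Start: model-based assignment applies "beyond the three initial patients who will receive the lowest dose of 42 Gy". Level 1 therefore always has at least 3 patients.
- Escalation: "we will require at least 3 sequential patients at each dose level, prior to escalating dose".
- Pause, once 3 sequential patients are at a new level: "enrollment will be paused until one of these patients experiences a DLT or a minimum of 3 months elapses".

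Section 7.2.1 makes everyone who starts radiotherapy evaluable. The suspension rule in 7.4 looks only at Level 1, and 7.3 plans no confidence intervals. Section 7.2.2 ties the secondary objectives to the declared level, for example "To evaluate the efficacy of the HART-HN regimen at the minimum number of safe fractions at 1-year".

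**The concern.** A TITE-CRM fits one curve to all patients, so it returns an estimated DLT rate for every level, including one that nobody received. That is acceptable for assigning the next patient. It is weaker as the sole basis for declaring a level safe, because the conclusion about that level then comes from the assumed shape of the curve.

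The main route is late follow-up. After the 18th patient is enrolled, DLT-free months raise the follow-up weights, and the final fit can move up to a level that was never assigned or had only just been opened.

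Delivery in as few as 5 fractions is the trial's stated hypothesis, and section 2 presents the result as the foundation for later comparative trials. A reader told that 5 fractions met the limit would expect that some patients had received 5 fractions. With no interval planned, nothing in the analysis plan would show otherwise. The level-specific summaries of efficacy and quality of life in 2.2 and 7.2.2 would also have almost no data.

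**Working it through.** **1. Does any rule bind the declaration?** The 3-patient rule counts patients at the level being left and governs the next assignment. The pause starts only after 3 patients are at a new level. The suspension rule concerns Level 1, and evaluability needs only the start of radiotherapy. None sets a number treated, or followed, at the declared level.

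**2. A path that ends in such a declaration.** Model: p = skeleton^exp(β), with β normal, mean 0 and SD 1.16 (variance 1.34). A DLT contributes p; no DLT contributes 1 − w·p, with w = months followed / 12. The rate is evaluated at the posterior mean of β. The empiric form is stated in 7.3; the skeleton (.10/.30/.50) and prior are assumptions.
- Data: 8 patients at Level 1 (no DLT; weights 0.75 and 0.20 for two, 1 for the rest), 10 at Level 2 (one DLT; weights 0.69, 0.85 and 0.51 for three without a DLT, 1 for the other six), none at Level 3.
- Posterior mean β = 0.608, so exp(β) = 1.837.
- Level 1: 0.10^1.837 = 1.5%. Level 2: 0.30^1.837 = 10.9%. Level 3: 0.50^1.837 = 28.0%.
- 28.0% is below 33% and is also the estimate closest to 33%, so either selection rule declares 5 fractions with nobody treated in 5 fractions.
- With all weights set to 1, the Level 3 estimate is 17% to 26% over five skeletons (.10/.30/.50, .05/.15/.30, .10/.20/.33, .10/.33/.45, .20/.33/.47). Each declares Level 3 if the rule is an estimate of at most 33%.

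**3. The plan's own figures.** Accrual: 18 / 1.5 per month = 12 months, as stated. Each row of the 7.3 table sums to 100%, for example 15.9 + 28.2 + 55.9 + 0.0 = 100.0. The simulations therefore had no outcome for too little data to declare. The table itself could not be reproduced: the best mean total-variation distance was 0.14 with the fit at full follow-up and about 0.10 with the fit at last enrolment. Because the inputs are not stated, this does not show the table to be wrong.

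**4. How often.** Simulation inputs from 7.1, 7.3 and 7.4: 18 patients, 1.5 per month, constant DLT hazard, 75.4% one-year survival with deaths censored, first 3 patients at Level 1, the 3-patient rule, the pause, and the 95% suspension rule. Assumed: the skeleton (up to 13 tried), the prior SD (1.16 main; 0.6 and 2.0 also tried), the selection rule (closest to 33%, or highest level at or below 33%) and the time of the final fit. Each setting had 1,000 to 5,000 trials.

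| Final fit | Declared level had 0 patients | Few patients |
|---|---|---|
| Full follow-up, first three profiles | about 1–13% | 2 or fewer: about 4–25% |
| Last enrolment | about 0–3.5% | 1–2: about 0.2–7% |

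In the 30/45/60 profile at full follow-up, 2 or fewer occurred in about 1 to 14%. In the 10/30/50 profile, where Level 3 is too toxic, 19 to 50% of Level 3 declarations rested on fewer than 3 patients there, and 10 to 31% on none.

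**5. Does a generous reading of the 3-patient rule help?** Suppose it also bound the declaration. With skeleton .10/.20/.33, the at-most-33% rule and the 10/30/50 profile, 0-patient declarations stay at 5.1% and 1–2-patient declarations go from 5.9% to 6.0%. Three patients at Level 2 still open Level 3.

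**6. What two patients show.** At a true DLT rate of 50%, no DLT in 2 patients has probability 0.5² = 25%. The one-sided 95% upper bound after 0 of 2 is 1 − 0.05^(1/2) = 78%.

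**7. Effect of a minimum of 3 treated, stepping to more fractions.** Skeleton .10/.20/.33, at-most-33% rule, full follow-up, 3,000 trials:
- 10/30/50: false Level 3 falls from 20.8% to 13.7%; correct Level 2 rises from 53.0% to 56.0%.
- 5/15/30: correct Level 3 falls from 65.8% to 55.9%.

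Over four skeletons and both selection rules, false Level 3 in 10/30/50 falls from roughly 14–40% to 11–32%. With .10/.30/.50 and the at-most-33% rule it falls from 7.3% to 5.7%.

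**The case against.** Borrowing across levels is how a TITE-CRM works, and the sponsor chose it knowingly. That stands: the point is not the borrowing, but a safety declaration with no data condition attached.

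The size depends on inputs the documents do not give, above all the time of the final fit. This also stands. A 12-month endpoint with 12 months of follow-up (7.2.1, 7.4) makes full follow-up the natural reading, but it is not written down, and at last enrolment the problem is much rarer. Hence both ranges.

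A minimum can be written badly. If it counted only patients with completed 12-month follow-up, three treated patients would all survive the year with probability 0.754³ = 43%. If the fallback were simply the level with the fewest fractions that meets the count, it could move below the number of fractions the model supports; in simulation this happened in about 1 to 7% of trials. The fix must exclude that.

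Two stronger readings are tempting and not supported:
- **That the design errs toward fewer fractions.** The 7.3 table does not show this. Its first two rows miss toward more fractions in 15.9 + 28.2 = 44.1% and 24.4 + 25.2 = 49.6% of trials; the third misses toward more fractions in 51.0% and toward fewer in 21.1%.
- **That the secondary endpoints would be empty.** Section 2.4 defines locoregional control and survival for everyone given HART-HN, and all patients are followed. Only the level-specific summaries in 2.2 and 7.2.2 would be thin.

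**Conclusion.** The point holds as a gap in the primary declaration rule. As written, Level 2 or Level 3 can be declared safe with 0 to 2 patients treated there; Level 1 is not affected. That no rule prevents this follows from the text and needs no assumption. Its frequency does: the ranges in the table above rest on an assumed skeleton, prior, selection rule and time of the final fit, and should be quoted only as ranges. At full follow-up it is not a rare accident, and at last enrolment it is uncommon but not excluded. The finding does not show that the 7.3 table is wrong or that TITE-CRM is unsuitable. It is a cheap improvement to the rule.

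**What to change.** Add to 7.2.1:
- The final TITE-CRM fit is made after 12-month follow-up is complete.
- A level can be declared only if its estimate in that fit meets the 33% limit and at least a stated minimum number of patients were treated at it. Three is an example, being the number already used in 7.1; the sponsor may choose another.
- If the indicated level fails the count, the declaration may move only to the next level with more fractions that meets both conditions, never to fewer fractions. The estimate for the untried or barely tried level is reported as a model projection.
- The number treated at the declared level, and the number followed to 12 months or to a DLT, are reported with the result.

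State the skeleton, prior and selection rule, and rerun the 7.3 table with this condition. If the minimum is set above 3, Level 1 may also fall short, so the text should say what is reported when no level qualifies.

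Cost: a short addition to 7.2.1 and a rerun of an existing simulation, with no extra patients and no change to dose assignment. With a minimum of 3 treated, correct Level 3 declarations in the 5/15/30 and 10/15/25 profiles fall by roughly 3 to 13 points; those lost rested on 0 to 2 patients. A larger minimum costs more: with 6, in the setting of step 7, correct Level 3 in 5/15/30 falls to 48.6% and correct Level 2 in 10/30/50 to 38.9%, with false Level 3 at 10.0%.

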- 1) The proposed regimens can be delivered in only **two weeks or less**, increasing compliance and tolerance for HNSCC patients and decreasing omission, delays or breaks in post-operative radiation, which represent major causes of disease relapse. Since substantial radiation toxicities do not typically begin until the third week of treatment, delivering post-operative radiation in only two weeks or less should lead to high compliance rates without treatment breaks. Further, HNSCC patients' ability to receive consistent post-operative radiation can be limited by travel distance and transportation challenges often related to social determinants of health including socioeconomic status, rural setting, and race. Patients of black race, Hispanic ethnicity, or with Medicaid insurance are significantly less likely to travel long distances for treatment. As such, these groups are less likely to receive care at academic and high-volume centers, more likely to have treatment breaks, and have worse survival outcomes. By condensing therapy from six weeks to two or less, this regimen will lessen the financial and psychosocial burden of radiotherapy and may reduce disparities in treatment and outcomes by facilitating greater access to care. Further, we have shown that in interviews of a subset of our patient population who refused adjuvant radiotherapy, 75% would have undergone radiation if it were completed in two weeks or less, leading us to select regimens that could be delivered in this time frame (10, 8 and 5 fractions).
- 2) These three regimens target a biologically effective dose (BED) will of ~100 Gy for an  $\alpha/\beta=3$  for all dose levels. An important risk of hypofractionated regimens is late toxicity to normal tissues. The design of these three proposed dose levels, however, maintains an acceptable BED to late-responding tissues that is consistent with the BED3 (100 Gy) of conventional postoperative radiation of 60 Gy in 30 fractions:

Total dose(Gy)/number of fractions	Dose per fraction (Gy)	a/b 10 (Gy)	a/b 3 (Gy)
42/10	4.2	59.64	100.8
39/8	4.875	58.01	102.3
32.5/5	6.5	53.6	102.9

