**Potential benefits of HART-HN: Easier access to care will lead to increased compliance with radiation and improved cancer control rates.** It is well-established that patients with advanced stage HNSCCs have improved LRC and survival with the addition of post-operative radiation as compared to surgery alone. However, while the critical importance of post-operative radiation has been known for decades, a large percentage of patients with advanced HNSCCs forego this life-saving therapy. In a preliminary study, our group analyzed the National Cancer Database (NCDB) from 2004-2015 and found that of 7,271 patients with surgically resected pathological stage III-IV oral cancer, **32% did not receive any post-operative radiotherapy and a further 14% did not finish the full course of radiotherapy (<60Gy conventional radiation).** These advanced oral cancer patients who did not receive indicated post-operative radiation therapy (PORT) or could not complete the full course of therapy had **significantly worse survival outcomes (Figure 1).** Omission or inability to complete radiation is frequently related to the long duration and extended toxicities of conventional therapy: six weeks of radiation is an immense physical, psychosocial, and financial commitment for patients to make immediately after a major operation. We hypothesize that if patients were offered HART-HN over two weeks or less instead of the conventional six-week course, a higher proportion would receive the full radiation treatment course, with critical implications for disease recurrence and survival. Six of the last eight HNSCCs patients at our institution who refused recommended post-operative radiation, indicated that they may have pursued treatment if offered over a shorter course. This is further supported by data from breast cancer showing adoption of hypofractionation has increased radiotherapy utilization, decreased wait times, and improved access to care.

**Figure 1. Association of Survival with PORT for advanced stage oral cancer.** Overall survival of 7,271 patients from the NCDB with pathological stage III-IV oral cancer stratified by adjuvant radiation dose and adjusted for covariates.

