**(Date)**

#### **4.7 Discontinuation of Study Treatment, Withdrawal, and Compliance**

Discontinuation from the study treatment does not mean discontinuation from the study. Subject will be considered in follow-up, study procedures should still be completed as indicated by the study protocol, and AEs/SAEs will continue to be reported according to this protocol.

In the absence of treatment delays due to adverse events, study treatment/intervention may continue until:

- Disease progression.
- General or specific changes in the subject's condition renders the subject unacceptable for further treatment in the investigator's judgment.
- Inter-current illness that prevents further treatment administration.
- Subject decides to withdraw from the study.
- The subject has significant noncompliance with the protocol (see below).
- Unacceptable adverse event(s) and/or dose level reduction beyond requirements as detailed in this protocol.
- Study stopping rules are met.

Subjects who sign the informed consent form, enroll and receive the study intervention, but subsequently withdraw, or are withdrawn or discontinued from the study will not be replaced.

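### The non-completion limb of the DLT has no attribution test, so radiation stopped by an unrelated illness counts as a DLT and biases level selection towards more fractions

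*Combined protocol and SAP*

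**What the plan says.** Section 7.2.1 builds the DLT from three limbs.

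- Non-completion: an "inability to complete radiation treatment within 30 days of the start of radiotherapy not deemed to be related to disease progression", to which the clause adds unrelated death. Only these two causes are excluded, and no relation to radiation or toxicity is required.
- Toxicity: qualified as "Grade 4+ toxicity) probably or definitely related to radiation treatment as deemed by the treating physician".
- Death: "a death within one year of treatment deemed probably or definitely related to treatment".

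The section later repeats that a death judged unrelated to radiation is not a DLT.

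Other passages fix what happens to a patient who stops early:

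- Section 7.2.1: "All patients who initiate radiation therapy will be evaluable for the primary endpoint as long as they initiate radiation therapy".
- Sections 4.7 and 7.4: patients who withdraw are not replaced.
- Section 7.1: censoring for toxicity is described only for death from disease progression.
- Section 4.7 lists, among the reasons treatment may end, "Inter-current illness that prevents further treatment administration", along with the subject's decision to withdraw and noncompliance.

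No section gives a separate route for a patient who stops radiation for a reason unconnected with it.

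**The concern.** Two limbs ask whether radiation caused the event and the third does not. An infection or cardiac event unrelated to radiation that ends the course is not progression and not death, so by the letter of section 7.2.1 it is a DLT. The repeated exclusion of unrelated death suggests that the DLT was meant to capture harm from radiation; this limb does not carry that through.

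Such an event enters the model early and at full weight. The plan says that follow-up is weighted but does not give the function. If weights are linear over 12 months (an assumption), an event-free patient at 3 months counts 3/12 = 0.25, while the non-toxic DLT counts in full. With 18 patients and three levels, one or two of these events could move the recommendation away from a fraction level that meets the safety limit.

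A side effect, not quantified here: under section 7.1 the pause after three patients at a new level ends at a DLT or after 3 months, so a non-toxic stop could also end that observation period early.

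**Working it through.** **1. Inputs.** From the documents: limit 33% at 12 months (7.1, 7.2.1); N = 18, three patients every two months, constant DLT hazard, one-year survival 75.4% (7.3); institutional benchmark 9.5%, Grade 4+ toxicity only (7.3). Neither that benchmark nor the constant hazard contains a separate component for early non-completion. Assumed: q, the chance that a patient stops for an unrelated reason and is counted as a DLT, taken from 1% to 10% and independent of toxicity.

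**2. The plan's own figures.** For true rates 5/15/30%, section 7.3 reports declaration of Levels 1, 2, 3 and stopping as 15.9%, 28.2%, 55.9% and 0.0%; for 10/15/25%, Level 3 is declared in 50.3%. The skeleton, prior SD and exact selection rule are not stated. About 90 combinations were tried; none reproduced all four rows of the table within 2 points, and the best was off by up to 16.8 points. The table is therefore neither confirmed nor called wrong.

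**3. Where a level crosses the limit.** Counted DLT rate = 1 − (1 − p)(1 − q), where p is the true toxicity DLT rate. Setting this to 0.33 gives q = 1 − 0.67/(1 − p).

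- p = 30%: 1 − 0.67/0.70 = 4.3%
- p = 25%: 1 − 0.67/0.75 = 10.7%
- p = 9.5%: 1 − 0.67/0.905 = 26.0%

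**4. How often it would happen.**

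| q | Expected in 18 (18q) | At least one in 18: 1 − (1 − q)^18 | At least one in first 3: 1 − (1 − q)^3 | Counted rate at p = 30% | Counted rate at p = 25% |
|---|---|---|---|---|---|
| 1% | 0.18 | 16.5% | 3.0% | 30.7% | 25.8% |
| 2% | 0.36 | 30.5% | 5.9% | 31.4% | 26.5% |
| 5% | 0.9 | 60.3% | 14.3% | 33.5% | 28.8% |
| 10% | 1.8 | 85.0% | 27.1% | 37.0% | 32.5% |

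**5. Effect on selection.** TITE-CRM simulation with the empiric model, linear weights, the section 7.3 accrual and survival, the 3-patient/3-month rule and the 95% suspension rule; 1000 runs per cell, Monte Carlo error about 1.5 points. Entries are the probability of declaring Level 3, at q = 0 and then q = 5%.

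| Assumed skeleton and selection rule | True 5/15/30% | True 10/15/25% |
|---|---|---|
| 0.05/0.15/0.30, closest to 33% | 81.7 → 60.8 (−20.9) | 77.3 → 55.9 (−21.4) |
| 0.20/0.33/0.46, closest to 33% | 81.0 → 59.8 (−21.2) | 76.8 → 55.0 (−21.8) |
| 0.33/0.45/0.57, highest at or below 33% | 61.0 → 38.5 (−22.5) | 55.1 → 34.3 (−20.8) |

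A second program (skeletons 0.15/0.24/0.33 and 0.20/0.33/0.46, prior SD 1.16, 600 runs, error about 2 points) gave losses of about 10 to 18 points at 5%, and from none to about 8 points at 1–2%. One skeleton is common to both programs and the losses still differ, so the size depends on settings that the plan does not report. At q = 5% selection moved away from Level 3 under every specification.

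**The case against.** A reader might infer that every stop for logistics or personal choice becomes a DLT. The text does not go that far. The limb speaks of an *inability* to complete and does not define it; a purely voluntary stop may or may not qualify. Treatment runs Monday to Friday (3.1), so ten fractions span at most 14 calendar days, and the 30-day window leaves 30 − 14 = 16 days of slack. Short transport problems are mostly absorbed. Section 1.2 does say that consistent post-operative radiation "can be limited by travel distance and transportation challenges", but it offers the short course as the remedy, and section 1.3 expects breaks to be unlikely.

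A reader might also take the statement that "a further 14% did not finish the full course of radiotherapy" as a rate for this trial. It is an all-cause national database figure for conventional treatment, which section 1.2 links to long duration and toxicity. It is not a non-toxic stop rate for a one- to two-week course and should not anchor q.

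The simulated baselines do not match the plan's 55.9% and 50.3%. In the 5/15/30% profile, 5% contamination lifts the counted rate at Level 3 to 33.5%, so part of the loss comes from judging a composite endpoint against a toxicity-only truth. That does not explain the 10/15/25% profile, where the counted rate is 28.8%, still inside the limit.

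Finally, counting unexplained non-completion is a defensible cautious rule when early toxicity and postoperative illness are hard to separate, and the selection bias is not towards shorter regimens. This stands as a reason to keep stops of unclear cause as DLTs. It does not justify counting a stop whose documented cause is unrelated.

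**Conclusion.** The gap is real and narrow. Under section 7.2.1 an unrelated intercurrent illness that ends radiation is a DLT, and no other section prevents this. Voluntary stops are ambiguous, which with 18 patients is itself a source of inconsistent DLT calls.

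The direction of the selection bias, towards more fractions, does not depend on the assumed skeleton; the size does. The firm figures are conditional arithmetic: the 4.3% crossing point for a level with 30% toxicity, and the 60% chance of at least one non-toxic DLT at an assumed 5%. Both rest on independence and on a rate that the documents do not supply. If completion is as high as the protocol expects, the effect may be small. The 10 to 23 point loss in correct selection at 5% is indicative only. The documents do not support a claim that the trial will reject a safe 5-fraction regimen, or that the table in section 7.3 is wrong.

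**What to change.** In section 7.2.1, extend the existing exclusion so that non-completion is not a DLT when its documented cause is unrelated to radiation. Keep non-completion of unclear cause as a DLT, which preserves the cautious intent. Say whether a purely voluntary stop is an inability to complete.

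In section 7.1, state that patients who stop for unrelated reasons are censored for the TITE-CRM at the time treatment stopped. Letting them go on accruing event-free weight would be anti-conservative: a patient who stopped after one of five fractions would build up to a weight of 12/12 = 1 at a level never delivered. With linear weights, censoring at half a month leaves 0.5/12 = 0.04. Adverse event collection continues after treatment stops under section 4.7, so the text should also say whether a later radiation-related event in such a patient enters the model.

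The cost is a sentence or two, an attribution judgment for each non-completer, and slightly less follow-up weight from those patients. The reasons that sections 4.7 and 7.4 require are for leaving the study, which section 4.7 separates from stopping treatment, so the case report form needs a field for the cause of non-completion.
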